Despite potential opportunities to deliver screening for underserved populations through FQHCs, many challenges exist. Available strategies for screening promotion have undergone limited development and evaluation among low income predominantly Spanish-speaking FQHC Latino patients. Further, it is unclear which strategies are best for increasing screening, and whether implementing multiple approaches (e.g. inreach delivered at point of a medical visit vs. outreach not requiring an in-person visit) would be superior to taking one approach alone for optimizing screening rates. To begin to address these challenges, we have conducted pilot work that has 1) established an academic-community CRC partnership between UCSD, SDSU, and SYHC; 2) established that FQHCs are keenly interested in understanding the best and most practical strategies for screening promotion; 3) identified (through key informant interviews of providers, clinic leadership, experienced *promotoras* (community health workers), and screening experts) key themes our interventions must address; 4) adapted previous effective materials used for mailed FIT outreach and patient navigation-based in-reach for screening promotion. Now, utilizing this comprehensive partnership and pilot work, we propose the following specific aims:

Aim 1: Among 648 Latinos age 50-75 years served by the SYHC FQHC, not up-to-date with screening, compare impact of 4 strategies on screening completion via a randomized controlled trial. The strategies will include: a) a patient-navigation-based, in clinic, inreach strategy, b) a mailed FIT outreach strategy (FIT outreach), c) inreach + FIT outreach, and d) usual care (n=162 per group).

Hypothesis 1a: *The inreach strategy (with or without FIT outreach) will be significantly superior to usual care*

Hypothesis 1b: *FIT outreach (with or without the inreach strategy) will be significantly superior to usual care*

Hypothesis 1c: *FIT outreach + the inreach strategy will be significantly superior to either strategy alone compared to usual care.*

Aim 2: Conduct a process evaluation to examine the interventions' reach, effectiveness, acceptability, feasibility, and sustainability following the RE-AIM framework.

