The proposed research is innovative because it seeks to identify pragmatic interventions required to optimize CRC screening in a Latino underserved population, is highly feasible, and, will allow us to determine whether a combination of outreach and inreach interventions are superior to either strategy alone for increasing CRC screening. Further, the community-based partnership approach of linking our academic medical center/NCI-designated comprehensive cancer center (UCSD), a research university/Hispanic-serving institution (SDSU), and a large community health center (SYHC) may serve as a model for developing and implementing evidence-based interventions for traditionally underserved populations. Indeed, successful interventions will be demonstration of intervention effectiveness will support adoption by the SYHC, and disseminated through the local, regional and national CHC networks (e.g., Council of Community Clinics, California Primary Care Association, and the National Association for Community Health Centers). Overall, the research has potential to reduce cancer disparities among Latinos and other underserved populations served by FQHCs and beyond.

RESEARCH PLAN

SIGNIFICANCE

Colorectal cancer (CRC) is the 2nd leading cause of cancer death in the United States (US). CRC accounts for over 136,000 new cancer diagnoses, and over 50,000 deaths annually ⁽¹⁾.

Screening can reduce CRC incidence and mortality, but is underutilized, particularly among underserved populations. Randomized trials and observational studies have demonstrated that screening with fecal occult blood testing (including the guaiac fecal occult blood test (gFOBT) and the fecal immunochemical test (FIT)), sigmoidoscopy, and colonoscopy can reduce CRC incidence and mortality ⁽²⁻⁷⁾. As a result, the US Preventive Services Task Force has recommended screening for all individuals after age 50 years. However, according to the National Health Interview Survey (NHIS) the national screening rate is 59%, far below the 70% Health People 2020 target ⁽⁸⁾. Moreover, screening rates are particularly low among underserved populations, such as Native Americans, Asians, Latinos, individuals living in rural areas, individuals with lower education and/or socioeconomic position, and the under-/uninsured ⁽⁹⁾. For example, the screening rate among the uninsured is just 21% ^(10, 11).

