The EHR will be queried 4 times over a 1 year period. At time of each query 1/4 of the target sample will be identified and randomized, and have the assigned interventions initiated. Each group will be followed for 12 months for the primary outcome: completion of any CRC screening test (guaiac fecal occult blood test, FIT, sigmoidoscopy, or colonoscopy), measured by evidence of screening documented within the EHR. Thus, the total recruitment period will last 12 months, and the duration through completion of 6 month follow up of all patients will be 24 months. Measurements will include demographic information (race, ethnicity, sex, and age), number and location of health center visits, primary provider, and comorbid medical conditions. In secondary analyses, we will determine whether screening rates vary across these characteristics, and also assess whether for significant interactions between characteristics and intervention effects.

Analytic approach and sample size, Aim 1. We estimated the sample size for 5 comparisons (usual care vs. inreach, usual care vs. outreach, usual care vs. inreach + outreach, inreach + outreach vs. outreach alone, and inreach + outreach vs. inreach alone), assuming $\alpha = 0.01$ across all groups and power ≥ 0.8 . For these assessments, we assumed the following rates of screening on follow up among individuals not up to date at baseline: 10% for usual care, 25% for inreach, 25% for outreach, 45% for inreach + outreach combined. The 10% rate for usual care and 25% estimate for outreach were conservative assumptions based on our previously cited work (30). The 25% rate for inreach was a conservative estimate based on observations that inreach interventions such as patient navigation have boosted screening completion (among patients referred for colonoscopy) by 41 to 78%. Finally, the 45% rate for both interventions combined was considered the minimal clinically significant difference that would justify implementing two different interventions for increasing screening. Under these assumptions, we computed need for a sample size of $n=648$ patients ($n=162$ for each group) to have sufficient power for all primary comparisons of interest.

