The primary outcome is completion of any CRC screening test (guaiac fecal occult blood test, FIT, sigmoidoscopy, or colonoscopy) within 12 months of randomization. The analytic approach taken will depend on whether or not an interaction exists between the outreach and inreach strategies on screening completion. If no interaction is present, screening rates for inreach vs. usual care and outreach vs. usual care will be compared using a Chi-square test of proportions, requiring $p < 0.01$ for statistical significance. If interaction is noted, we will compare screening rates with a Chi-square test of proportions for inreach without outreach vs. usual care, as well as inreach with outreach vs. usual care separately, using a $p < 0.025$ to indicate statistical significance. In both cases (interaction or no interaction), secondary comparisons will include inreach plus outreach vs. usual care, as well as inreach plus outreach vs. either strategy alone. We will conduct additional analyses treating screening completion as the dependent variable, and examine the relationship of group assignment, demographic characteristics, primary provider, and clinic visit frequency to this outcome. Factors associated with screening completion on univariate analyses will be considered as part of a logistic regression model examining factors independently associated with screening completion; in the case of interaction by group assignment a term for interaction will be included in our models. Additionally, interactions between other factors (e.g. gender, age, language preference, income, inreach strategy and frequency of clinic visits) will be considered.

Approach, Aim 2 Process Evaluation. Following the RE-AIM framework(41-43), a quasi-experimental process evaluation of intervention programs is proposed as part of the research protocol using validated measures developed in previous studies(44). This process evaluation is designed to examine the intervention’s acceptability, feasibility, and sustainability(45-47). Process measures include: intervention fidelity, recruitment and retention issues, dosage delivered and received, participant satisfaction, and *navigator* perceptions on areas for improvement in each one-on-one session. [name], [name], and [name] will lead trainings to ensure intervention fidelity and standardized intervention delivery and dosage.

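### The Aim 1 analysis does not test the five comparisons sized as primary at 0.01: both Hypothesis 1c tests become secondary with no level, and the interaction branch lists no test of outreach alone against usual care

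*Combined protocol and SAP*

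**What the plan says.** All of this is in the protocol's section on the analytic approach and sample size for Aim 1, read with Hypotheses 1a to 1c in Specific Aims.

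**Sizing paragraph.** "We estimated the sample size for 5 comparisons (usual care vs. inreach, usual care vs. outreach, usual care vs. inreach + outreach", and then "inreach + outreach vs. outreach alone, and inreach + outreach vs. inreach alone". Alpha is 0.01 and power at least 0.80. The assumed rates are 10% (usual care), 25% (each single strategy) and 45% (combined). The paragraph ends with 162 per group "to have sufficient power for all primary comparisons of interest". It also says that "the 45% rate for both interventions combined was considered the minimal clinically significant difference that would justify implementing two different interventions for increasing screening".

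**Analysis paragraph.** The tests depend on whether inreach and outreach interact.
- No interaction: inreach vs usual care and outreach vs usual care, each at p<0.01.
- Interaction: inreach without outreach vs usual care, and inreach with outreach vs usual care, each at p<0.025.
- Either way: "secondary comparisons will include inreach plus outreach vs. usual care, as well as inreach plus outreach vs. either strategy alone", with no level.

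**Hypotheses.** 1b: "FIT outreach (with or without the inreach strategy) will be significantly superior to usual care". 1c: "FIT outreach + the inreach strategy will be significantly superior to either strategy alone compared to usual care". Specific Aims also says that the trial will show "whether a combination of outreach and inreach interventions are superior to either strategy alone for increasing CRC screening".

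**The concern.** The two paragraphs describe different test families. The two Hypothesis 1c comparisons are sized as primary and then analysed as secondary without a level, although they bear directly on whether two interventions are worth running together. Their level could therefore be settled after the data are seen. Nor does the analysis paragraph say whether 1c needs a win over both single strategies or over only one.

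In the interaction branch, a contrast that was sized and bears on Hypothesis 1b (outreach alone vs usual care) has no listed test. Combined vs usual care has two statuses there.

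The no-interaction branch has a further ambiguity. Its two tests could be single-arm contrasts, or pooled contrasts in the sense of the with-or-without wording of Hypotheses 1a and 1b. Only the single-arm contrasts were sized.

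**Working it through.** **1. Reproduce the sample size.** Inputs from the sizing paragraph: alpha 0.01, power 0.80, equal groups, rates as above. Sidedness is not stated. Two-sided is taken because it reproduces the stated figure.

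n = [2.5758·√(2·p̄·(1−p̄)) + 0.8416·√(p1(1−p1) + p2(1−p2))]² / d², where d = p2 − p1 and p̄ is the mean of p1 and p2

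For 10% vs 25%: (1.3841 + 0.4434)² / 0.15² = 148.4.

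With continuity correction: (148.4/4)·[1 + √(1 + 4/(148.4 × 0.15))]² = 161.5, so **162**, and 4 × 162 = 648.

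By the same formula, 25% vs 45% needs 142 and 10% vs 45% needs 43. A one-sided test would give 141 for 10% vs 25%. Splitting 0.01 over five tests (0.002 each) would give 210. The stated 162 therefore fits two-sided 0.01 per comparison, and 5 × 0.01 = 0.05.

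**2. Follow each sized comparison into the analysis paragraph.**

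| Sized at 0.01 as primary | No interaction | Interaction |
|---|---|---|
| Inreach vs usual care | 0.01 (single-arm or pooled unclear) | 0.025 |
| Outreach vs usual care | 0.01 (single-arm or pooled unclear) | not listed |
| Combined vs usual care | secondary, no level | 0.025, and also secondary |
| Combined vs outreach | secondary, no level | secondary, no level |
| Combined vs inreach | secondary, no level | secondary, no level |

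Nominal alpha with a stated level is 2 × 0.01 = 0.02 without interaction and 2 × 0.025 = 0.05 with it. In the interaction branch, adding the two 1c tests at 0.01 gives 0.07, and adding outreach alone at 0.01 gives 0.08.

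**3. Chance of any false positive.** Simulation: 1,000,000 trials, 162 per arm, all arms at 10%, uncorrected two-sided chi-square tests. Assumptions: single-arm contrasts in the no-interaction branch; an interaction test at 0.05, whose level and scale the protocol does not give; combined vs usual care counted once, at 0.025, in the interaction branch.

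| Plan | Any false positive |
|---|---|
| Five tests at 0.01 | 4.0% |
| As written, secondary tests at 0.01 | 4.1% |
| As written, secondary tests at 0.025 | 7.4% |
| As written, secondary tests at 0.05 | 13.6 to 13.7% |

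For 1c alone, with all three active arms at 25%, the combination falsely beats at least one single strategy in 1.0%, 2.3% or 4.5% of trials at 0.01, 0.025 or 0.05. If it must beat both, false support was at most about 2.5% in the scenarios run, even at 0.05.

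**4. How often the interaction branch is entered.** Rates 10/25/25/x, interaction test at an assumed 0.05.

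| Combined rate x | Additive scale | Logit scale |
|---|---|---|
| 25% | 66% | 77% |
| 30% | 34% | 55% |
| 35% | 12% | 33% |
| 45% (planned) | 12% | 7% |
| 50% | 33% | 5% |
| 60% | 85% | 18% |

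**5. Power at 162 per group, two-sided, no continuity correction.** Power = Φ{[d√162 − z·√(2p̄(1−p̄))] / √(p1(1−p1) + p2(1−p2))}.
- 10% vs 25% at 0.01: (1.9092 − 1.3841)/0.5268 = 0.997, giving 84%. At 0.025: 91%.
- 25% vs 45% at 0.01: (2.5456 − 1.7375)/0.6596 = 1.225, giving 89%.
- 10% vs 45% at 0.01: above 99%.
- Combination beats both single strategies at the planned rates (simulated): 82% at 0.01, 94% at 0.05.

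**The case against.** **The 0.01 carries over.** Both paragraphs sit in one section, and 0.01 is given for exactly these five comparisons. On that reading the whole plan gives 4.1% against 4.0%, which is no material difference. This stands as far as error inflation goes. It does not settle the level, because the analysis paragraph departs from 0.01 in one branch.

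**The regression covers the missing contrast.** The additional logistic analysis includes group assignment, with an interaction term if interaction is present. Such a model could estimate outreach alone vs usual care, so the contrast is not out of reach. But no contrast or level is stated and the analysis is an additional one, so it does not replace the test.

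**The interaction branch is rare.** At the planned rates this is right: 7 to 12% of trials. It becomes common if the combination adds little. A reader might infer that the branch is entered mainly in that case. That holds only for combined rates of 45% or below, because on the additive scale entry also climbs under strong synergy.

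**All five comparisons are listed without interaction.** This is correct if the two comparisons with usual care are single-arm. The fault in that branch is then status and level, not omission. In the interaction branch, combined vs usual care does have a level, 0.025, so the gap there is its double status.

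**Conclusion.** The mismatch is real and should be fixed. The analysis paragraph changes the status of both 1c tests and of combined vs usual care, changes the level in one branch, and leaves one sized contrast without a listed test. No other part of the protocol repairs this. Confidence is high for the textual mismatch, but not for the size of its consequences.

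Two stronger readings are not supported. A reader might infer that the plan inflates the false-positive rate. The figures of 7.4% and about 14% need secondary levels that the protocol never states, and 4.1% is equally compatible with the text. A reader might also infer that the trial is undersized. It is not: 162 per group is right for the five comparisons as sized.

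The branch-entry and gated error figures rest on an assumed 0.05 interaction test and on the single-arm reading of the no-interaction tests.

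**What to change.** In the analysis paragraph for Aim 1, for both branches:

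1. Name the five single-arm pairwise comparisons of the sizing paragraph as the primary family, each at two-sided p<0.01, replacing 0.025.
2. Define inreach and outreach vs usual care as the single-strategy arms vs usual care. Report any pooled with-or-without comparison as supportive.
3. Add outreach alone vs usual care to the interaction branch, and list combined vs usual care once.
4. Delete the sentence on secondary comparisons.
5. State that Hypothesis 1c is supported only if the combination beats both single strategies.

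**Cost.** Wording only; the total stays 648. At the planned rates each comparison keeps at least 80% power: about 84% for each single strategy vs usual care, 89% for each 1c test, and above 99% for combined vs usual care. Inreach vs usual care in the interaction branch falls from about 91% to 84%. Power to beat both single strategies is about 82%, against 94% at an assumed 0.05. At a 40% combined rate, below the 45% that the protocol treats as the minimum, it is 47% against 73%. The 0.01 is chosen to match the sizing. The both-wins rule alone would allow a higher level per test for 1c, if the sponsor prefers to state one.

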Successful organized strategies to increase screening among underserved populations (including Latinos) may involve inreach and outreach approaches. Organized screening requires an “explicit policy in a defined target population with a defined implementation and quality assurance structure, and tracking of cancer in the population.”^(9, 20) Organized screening strategies may broadly be categorized as inreach vs. outreach based on whether health care visits are required to deliver screening invitations ⁽⁹⁾. Inreach strategies promote screening at point of routine medical care. Outreach strategies target all eligible individuals within a defined population regardless of scheduled health care visits. Inreach strategies take advantage of in-person encounters with age-eligible individuals, but may be limited in reach due to requirement for health system visits, as many individuals do not access health care on a regular basis. Further, resources required to implement inreach strategies to promote screening among all eligible individuals may be substantial. Outreach strategies have the advantage of reaching a greater proportion of the population, with a centralized, potentially smaller team, but in theory might be less effective than interventions that occur in context of a face-to-face healthcare visit.

Examples of successful inreach approaches have included provider assessment and feedback, one-on-one education, patient navigation to promote colonoscopy completion after referral, and offering gFOBT or FIT at time of flu vaccination ⁽²¹⁻²⁷⁾. In a single SYHC clinic, we previously piloted delivery of one-on-one patient education for Latino patients using a culturally linguistically tailored CRC self-help brochure containing information on risk factors, knowledge, culture-bound myths and screening tests, with and without scripted review of key points within the brochure by a community health advisor prior to a primary care visit ⁽²⁸⁾. Compared to usual care, the brochure increased screening knowledge, and also increased frequency of discussion of screening with providers by 20%, but no differences were noted between delivery of the brochure with or without intense review. These results complement prior work that has shown one-on-one education to be effective in promoting screening ⁽²¹⁾. The main limitations of our prior work include small sample size (n=130 completed pre and post intervention surveys) and use of a surrogate outcome (knowledge rather than

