RCT inclusion/exclusion criteria. We will **include** individuals age 50 to 75 years, with one or more SYHC visits in the last year, at average-risk for CRC but not up-to-date with screening, insured by a MediCal provider, Medicare, or private health insurance. We will **exclude** individuals with personal history of CRC or colorectal polyps, as well as the uninsured. Uninsured individuals will be excluded because in absence of health insurance, we cannot guarantee that screening (and cancer care if CRC is found) will be financially possible. Inclusion and exclusion criteria will be applied through queries of the SYHC EHR.

Identification of candidate patients and recruitment. Using the SYHC EHR we will enroll and randomize 648 individuals meeting inclusion/exclusion criteria: 162 to usual care, inreach, mailed FIT outreach, and the

inreach strategy plus FIT outreach, respectively (see sample size and power calculations below). A waiver of documentation of informed consent will be obtained for randomization and intervention delivery based on two primary factors: 1) goal of increasing screening for as many individuals as possible, and 2) scientific advantage of observing as close to “real world” impact of the planned strategies on a sample of patients. We reviewed with our Institutional Review Board a potential strategy for complete waiver of informed consent, but were advised that maximizing patient autonomy and awareness of potential loss of confidentiality associated with research data collection merited at minimum a one-page informational research “fact sheet” that would provide patients with information about the research project. In the letter, patients will be the option to specifically note a desire not to participate in the intervention or subsequent data collection. Recruitment will continue until a sample size of 162 individuals per group who do not opt out of the research is achieved. In our primary, intent to screen analysis, we will analyze all randomized individuals who do not opt out of the research.

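### The secondary logistic model picks covariates by univariate screening on its own outcome and leaves the window for clinic visit frequency undefined

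*Combined protocol and SAP*

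**What the plan says.** All references are to the combined protocol and SAP.

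- **Status and content of the model** (Analytic approach and sample size, Aim 1). After the chi-square comparisons the plan adds: "We will conduct additional analyses treating screening completion as the dependent variable". These analyses will "examine the relationship of group assignment, demographic characteristics, primary provider, and clinic visit frequency to this outcome".
- **Selection rule** (same section). "Factors associated with screening completion on univariate analyses will be considered as part of a logistic regression model". The stated purpose is "examining factors independently associated with screening completion". No p-value threshold is given, and no term is said to be kept regardless of the screen. An arm interaction term is added only if an interaction is found.
- **Interactions.** The same section names visit frequency and inreach strategy among the factors whose interactions will be considered. The paragraphs on identification and recruitment also plan tests of whether patient characteristics modify the intervention effects.
- **Measurement of visits** (identification and recruitment). Besides race, ethnicity, sex and age, the trial records "number and location of health center visits, primary provider, and comorbid medical conditions". No time window is attached.
- **A baseline count exists.** The inclusion criteria take from the EHR patients "with one or more SYHC visits in the last year".
- **Link between inreach and visits** (Significance). "Inreach strategies promote screening at point of routine medical care". The documents do not say that inreach raises or lowers the number of visits.

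**The concern.** There are two separate problems, with different consequences.

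**Selection on the outcome.** A factor enters because its association with screening looked strong in these data, and the same data then supply its p-value and interval. The second look is not independent of the first. Chance findings survive, and real associations that survive tend to be overstated. A factor that matters only jointly with others can be lost. Since the model exists to name independent factors, this affects its main product.

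**Visit frequency without a window.** A count taken before randomization is an ordinary baseline covariate. A count taken during follow-up is not, because it can be affected by treatment. If inreach and navigation generate contacts, adjusting for follow-up visits removes part of the inreach effect. It also makes the arms non-comparable on whatever drives both visits and screening, such as general engagement with care. The count might also be partly a result of screening: the outreach description under Pilot Research has FIT results given by phone and in person. In either case an inreach-by-visits interaction would no longer be a clean subgroup result.

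The health center could use these results to decide which patients should get which strategy.

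**Working it through.** **1. The plan's own figure, and whether it depends on this model.** Inputs from the Aim 1 analysis section: 10% vs 25%, alpha 0.01 (taken as two-sided), power 0.80.

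- Pooled rate = (0.10 + 0.25)/2 = 0.175.
- n = [2.576·√(2·0.175·0.825) + 0.842·√(0.10·0.90 + 0.25·0.75)]² / 0.15² = 148.4, so 149.
- With continuity correction: (148.4/4)·[1 + √(1 + 4/(148.4·0.15))]² = 161.5, so **162 per group**, the plan's figure.

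The sample size rests on an unadjusted comparison of two proportions. Nothing in the logistic model enters it.

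**2. Univariate screening.** The documents name ten candidates besides arm: race, ethnicity, sex, age, number of visits, location of visits, primary provider, comorbid conditions, language preference and income. Assumptions: threshold 0.05 (not stated in the plan), independent factors, one test each.

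- Expected false selections among k null factors: 0.05·k.
- Chance of at least one: 1 − 0.95^k.

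| Null factors among the ten | Expected false selections | Chance of at least one |
|---|---|---|
| 5 | 0.25 | 1 − 0.95⁵ = 23% |
| 10 | 0.50 | 1 − 0.95¹⁰ = 40% |

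A null factor selected at p<0.05 has, in that univariate fit, a 95% interval that excludes an odds ratio of 1 by construction. Refitting with the other selected factors changes this little: in a simulation with ten null factors, intervals of selected factors covered the truth about 4% of the time. That figure mostly restates the selection rule. The 0.25 to 0.50 false factors per trial is the more useful size.

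**3. Visit window.** This is an illustration with 1,000,000 simulated patients per row. None of the following inputs comes from the documents:

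- An unmeasured engagement score u is standard normal.
- Visits are Poisson with mean exp(0.7 + 0.4u) before randomization. During follow-up the mean is the same, multiplied by a factor under inreach.
- Log-odds of screening = −2.6 + 1.1·inreach + 1.1·outreach + 0.5u + 0.1·(follow-up visits).

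| Effect of inreach on follow-up visits | Inreach OR, no visit term | Adjusted for baseline visits | Adjusted for follow-up visits |
|---|---|---|---|
| None | 2.80 | 2.85 | 2.90 |
| ×1.25 | 2.94 | 2.99 | 2.67 |
| ×1.5 | 3.10 | 3.17 | 2.50 |
| ×2 | 3.43 | 3.52 | 2.22 |

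The coefficient of inreach at a given number of visits is 1.1 in every row. Even so, the last column falls from 2.90 to 2.22. Removing the effect that runs through visits therefore does not explain the whole drop; the rest is distortion through the shared engagement score. With baseline visits the small upward shift fits the usual non-collapsibility of the odds ratio.

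**4. If screening itself adds visits.** A separate simulation, also on assumed inputs, let a completed screen add one visit with probability 0.25 to 1. The odds ratio for visit frequency rose from about 2.3 (baseline count) to between 2.8 and 5.9, while the inreach odds ratio barely moved. Under this mechanism the factor result is what mainly goes wrong.

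**The case against.** The case for leaving the plan alone has real weight.

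- **The measurement list can be read as baseline.** Visits stand beside race, sex, age, provider and comorbidities, and the next sentence treats the list as patient characteristics that may modify the effect. Prior-year visits are already drawn for eligibility. On that reading the visit problem disappears. This stands as a plausible reading, but the plan does not commit to it.
- **Inreach may not change visit counts.** The Significance section describes inreach as using encounters that already occur. The navigation described there is largely by telephone, and diagnostic colonoscopy is referred outside the health center. This also stands: an effect on visits is an inference.
- **Visit frequency may not enter.** Factors passing the screen are only considered. That gives little protection, since a variable tied to engagement is likely to pass.
- **The model is secondary.** Intervention effects are judged by chi-square tests. This stands fully and limits the consequence.

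A reader might infer three stronger things that are not supported. The first is that the adjusted effects would necessarily be biased. That needs a follow-up count, an effect of inreach or screening on it, and its entry into the model; the documents establish none of these. The second is that adjustment could reverse the inreach effect. The lowest odds ratio in the table is 2.22, attenuated but well above 1. The third is that univariate screening biases the arm comparison. Choosing among baseline covariates does not by itself confound a randomized contrast.

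**Conclusion.** The point holds in two parts of unequal certainty.

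The selection rule is stated in the plan, and following it gives over-favourable p-values and intervals for the factors reported as independent. Its size depends on the threshold and on how many candidates are truly unrelated to screening: with five to ten null factors at 5%, 0.25 to 0.50 false factors per trial.

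The visit-frequency part is conditional. The window is undefined, so the adjusted inreach effect and the inreach-by-visits interaction could be distorted, but only if visits are counted after randomization and are changed by inreach or by screening. The documents give no figure for such a change. The illustration runs from almost no difference (2.85 vs 2.90) to a clear attenuation (3.52 vs 2.22 when visits double), and other assumptions would give other numbers.

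The primary chi-square comparisons and the sample size of 162 per group (648 total) are unaffected. The change is worth making because it is nearly free and protects the stated purpose of this model.

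**What to change.** In the Aim 1 analysis section:

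1. Replace univariate screening with a pre-specified list of baseline factors, for example age, sex, language preference, clinic location, prior-year visits and enrolment wave (the four EHR queries). Fix clinic location as of randomization. Language preference appears in the plan only among the interaction factors, so confirm that the EHR extract contains it.
2. State that randomized arm is always in the model.
3. Define visit frequency as visits in the 12 months before randomization, for both adjustment and interaction tests.
4. Report follow-up visits by arm descriptively if wanted, for example in the Aim 2 process evaluation.

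The cost is a few sentences. Prior-year visits are already queried from the EHR for eligibility, and neither the sample size nor any primary comparison changes.
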